#### COVID-19 Policies.

We will offer all participants in the intervention arm HIV and HCV testing. Research staff will perform testing as described above in the office. However, if a participant prefers, we will help them perform the test using a self-test kit, or we we will make a referral to a local health department.

Testing is offered in the local health departments through UK's Kentucky Income Reinvestment Program (KIRP) with UK staff based at the health departments. The Kentucky Cabinet for Health and Family Services' Department for Public Health and UK established KIRP to improve health care delivery via disease education, prevention, treatment and professional services for persons living with HIV through collaborations with existing Ryan [name] HIV/AIDS funded programs and harm reduction programs at local health departments. Testing is offered through collaboration with the harm reduction programs.

For participants who prefer to test themselves, we will offer home-based (self-test) HIV and HCV testing and drug screening to be completed in-person at the study office. If the participant does not feel comfortable coming to the office or all research activities are remote only due to COVID-19 restrictions, we will offer to meet the participant at a mutually agreed-upon location or their home to complete home-based (self-test) HIV and HCV testing.

For home-based (self-test) HIV testing we will use FDA-approved OraQuick In-Home HIV Test (OraSure Technologies, Inc., Bethlehem, PA) that tests for HIV antibodies in human saliva (gum swab) with 91.67% sensitivity and 99.9% specificity, with results ready in 20 minutes. For home-based (self-test) HCV testing we will use EverlyWell HCV human antibody test (Everlywell, Inc., Austin, TX), which requires finger stick to obtain blood for a dry spot sample that will be mailed to a laboratory for processing. Both sensitivity and specificity for this test are above 99%. We will conduct saliva drug test using SalivaConfirm (TestCountry, San Diego, CA) drug screening kit that detects 10 types of illicit drugs in the sample in 10 minutes.

After the baseline survey, if the participant does not feel comfortable coming to the office or all research activities are remote only due to COVID-19 restrictions, the REHN will meet the participant at a mutually agreed-upon location or at their home. The REHN will bring a biological test kit (HIV, HCV and drug tests) and harm reduction kit (nasal Naloxone spray, Naloxone brochure, Good Samaritan and Naloxone Laws, resource guide, information on incentive card and Certificate of Confidentiality). The REHN will drop the package off at the participants' home (placing the kit on a porch or car hood to permit social distancing) or will meet at a mutually agreed-upon location that is safe, following social distancing rules to avoid COVID-19 exposure for participants and staff. If the REHN is conducting

HIV/HCV testing, the REHN will conduct pre-test HIV/HCV counselling over the phone. The participant will be asked to collect biospecimens (oral swabs for HIV and drug testing, finger stick for HIV testing) in their home or at a mutually agreed-upon location that is safe (e.g. a gas station restroom or in their car). The participant will provide the completed test kits to the REHN following social distancing rules (e.g., placing the completed kits on their porch or the REHN's car hood). The drug test and HIV test will be read by the REHN, while HCV test will be sent to a lab for processing. If HIV or HCV tests are positive, the participant will be referred to the Department of Health for confirmatory testing.

During 3-month and 6-month data collection waves we will conduct drug screening only, so the REHN will bring drug screening kit only.

#### CQI

Interview guides for the qualitative interviews are attached.

6/28/22 Modification: We will drop the 6-month survey for newly recruited participants once approved by the IRB.

Attachments	
Attach Type	File Name
DataCollection	Qualitative Interview Guide 040222 - Pharmacist.pdf
DataCollection	Qualitative Interview Guide 040222 - REHN.pdf
DataCollection	Baseline Survey Part 1 081721 - Clean.pdf
DataCollection	Baseline Survey Part 2 081721 - Clean.pdf
DataCollection	3 Month Survey 051021 - Clean.pdf
DataCollection	6 Month Survey 061121.pdf
DataCollection	Locator 031821 - Clean.pdf
DataCollection	Security Assessment 111820 - Clean.pdf
DataCollection	Timeline Follow-Back.pdf
DataCollection	Script for Rehab and Others Facilities 013120.pdf
DataCollection	Qualitative Interview Guide 062822 Participants - Clean.pdf

#### Resources

Describe the availability of the resources and adequacy of the facilities that you will use to perform the research. Such resources may include:

- Staffing and personnel, in terms of availability, number, expertise, and experience;
- Computer or other technological resources, mobile or otherwise, required or created during the conduct of the research;
- Psychological, social, or medical services, including equipment needed to protect subjects, medical monitoring, ancillary care, or counseling or social support services that may be required because of research participation;
- Resources for communication with subjects, such as language translation/interpretation services.

This study will involve the PIs, co-investigators, a project director, project coordinator, community-based research assistants, a research assistant from the College of Public Health, and community-based Re-entry Health Navigators (REHNs). The PIs and research staff will be responsible for scheduling surveys, submitting IRB modifications, conducting all surveys, filing consent forms, and managing incoming data, uploading data to a secure server, and assuring data quality and protection of human subjects. The study will have a UK leased field offices in Morehead and Hazard that houses a project coordinator and community researchers and a retention coordinator, and UK-leased offices in local departments of health staffed by REHNs.

#### Potential Risks & Benefits

##### Risks

- Describe any potential risks – including physical, psychological, social, legal, ability to re-identify subjects, or other risks. Assess the seriousness and likelihood of each risk.
- Which risks may affect a subject's willingness to participate in the study?
- Describe likely adverse effects of drugs, biologics, devices or procedures participants may encounter while in the study.
- *Qualitative research* - describe ethical issues that could arise while conducting research in the field and strategies you may use to handle those situations.
- Describe any steps to mitigate these risks.

##### Benefits

- Describe potential direct benefits to study participants – including diagnostic or therapeutic, physical, psychological or emotional, learning benefits. This cannot include incentives or payments.
- State if there are no direct benefits.
- Describe potential benefits to society and/or general knowledge to be gained.

Describe why potential benefits are reasonable in relation to potential risks. If applicable, justify why risks to vulnerable subjects are reasonable to potential benefits.

The procedures to be used by this study will involve conventional social science research methods that are routine in studies of this type. The potential psychological risks will be discussed with participants to assist them in making an informed decision as to whether they wish to participate in the survey. These potential psychological risks are primarily related to being asked questions in the surveys about illegal behaviors that they do not feel comfortable answering. There is also a risk that there may be a breach of confidentiality of their survey. Every effort will be taken to ensure that this does not happen. No files – hard copy or electronic – will be stored in the jail. REHN records for client sessions will be completed and stored in the research field office. Confidentiality issues will be stressed during informed consent, which will include the description of a federal Certificate of Confidentiality, which provides an additional layer of human subject protection. Participants will also be assured that their survey answers will not be made available to any representative of the jail or criminal justice system.

Of note, the KY Department of Corrections does require that all incarcerated individuals complete a general DOC consent form granting permission to participate in research and require that a copy of that consent form be deposited with the KY DOC headquarters. To protect participant confidentiality and avoid revealing to DOC staff who screened eligible and participated, we will administer the DOC consent form to all individuals attending the study overview session, rather than only to those who screen eligible. Therefore, jail officials and administrators will not be able to decipher which participants screened eligible, participated, or refused to participate. It is possible, that a study participant may experience anxiety, emotional distress, or other negative reactions due to the content of the screening questions. Based on our experiences working with this population, such occurrences are rare. However, with the participant's permission, they will be referred to the medical staff at the jail for additional help and support related to psychological distress. The Community Resource guide also contains information on mental health and substance abuse services in the community.

Potential psychological risks will be communicated during the informed consent process to help people make an informed decision as to whether they wish to participate. Some participants may be uncomfortable about discussing drug-related health concerns, social service needs, and related goals with REHNS; connecting with services at unfamiliar agencies may also be challenging, particularly if staff at those agencies stigmatize them for their substance use disorder. They may also be uncomfortable answering personal questions about stigmatizing and in some cases illegal behaviors (drug use, condomless sex), health outcomes (ODs, HIV, HCV), and PWUD-related healthcare service use. If these data, or data on the results of the urine test administered at baseline, were accessed by people outside of the study, the participant could experience legal actions, social stigma, or other social sanctions (e.g., job loss). The START intervention may also cause distress, as participants seek to reconcile goals with realities, and discuss personal sexual and drug-related behaviors. In addition, individuals who test positive for HIV or HCV may experience considerable distress. If confidentiality were breached, participants may experience stigma, lose their job or housing, or be ostracized.

Participants in the intervention group will receive the nasal spray naloxone (Narcan) to carry with them in case they encounter someone who has an opioid overdose or in case they have an opioid overdose and a friend can use the naloxone to respond. Additional naloxone will be given to participants in the event that they use/lose their Narcan, enter treatment, then leave treatment and have no Narcan. Research staff will show a short video that shows how to use the naloxone kit and perform rescue breathing. Research staff will answer questions and will provide a handout explaining how to use it and possible side effects (see attached Naloxone handout; note: this is the same handout approved by Kentucky Pharmacists Association for use by pharmacists when distributing naloxone). In the consent form, participants are informed that naloxone temporarily reverses the effects of opioid overdose and is not a substitute for emergency medical care and that they should call 911 if they witness an overdose. They are also informed that naloxone can cause side effects, including but not limited to sudden opioid withdrawal symptoms and that the signs and symptoms of an opioid emergency can return after the nasal spray is given. They are also informed that naloxone only works on opioid-related overdoses and has no effect on people who are not using opioids. Witnessing an overdose can cause physical, psychological, or emotional problems such as anxiety or depression. If a participant administers naloxone, they may experience additional physical, psychological, or emotional problems because the naloxone effects may wear off and overdose symptoms could return, the person may experience side effects, and/or the person may become irritable or violent. These risks are explained in the consent form. In addition, the consent form explains that Kentucky's Good Samaritan law is supposed to protect them from being charged or prosecuted for drug or paraphernalia possession if they call 911 because they witness an overdose and stay with that person. But in rare cases, law enforcement may arrest them if you have warrants for another crime or if they have a search warrant or if they are unfamiliar with the law. Participants are also informed that if people find out that they have naloxone, it might cause embarrassment and could hurt their standing with people in the community who have a negative attitude toward people who use drugs and/or toward naloxone.

Comparison group: Protocols will be identical to those described for the intervention group, but the comparison group members will not take part in any intervention aside from the naloxone training, including HIV or HCV testing. Risks and benefits will be limited to those pertaining to data collection, as described above.

**Collection of Biological Specimens:** The biological procedures to be used by this study will involve conventional medical research methods that are routine in studies of this type. The potential psychological risks will be discussed with participants during the consent process to assist them in making an informed decision as to whether they wish to participate in this part of the study. First, there is the potential for receiving a "false positive" on HIV/HCV testing. This potential is statistically remote because every positive HIV/HCV test result will be confirmed through a confirmatory test. Second, depression is likely when a subject receives a positive result. Similarly, there are emotional liabilities in some cases associated with receiving a negative test result (relief versus survivor's guilt). In either case, post test counseling will be provided and referral to the appropriate human service resources will be offered. The potential risks for a subject revealing her positive serostatus, or experiencing a breach of confidentiality, will also be discussed during post test counseling. These risks involve loss of employment or insurance, rejection by family or friends, and others. The immediate risks associated with the finger pricks and blood draw are slight pain and local bleeding at the site, and are comparable to those incurred during routine medical care.

**Intervention group participants:** The proposed study has potential benefits. First, individuals will have opportunity to be screened for risk behavior including injection drug use and risky sexual activity and receive feedback on results. Second, the study REHN will share important prevention intervention information with high-risk PWUD during the transition from jail to the community with the overall goal of reducing risk behavior and increasing community service utilization. Third, participants will receive an interactive training with animated

scenarios and narration on preventing, recognizing, and responding effectively to an opioid OD, accompanied by information about Kentucky's Good Samaritan Law and Naloxone Access Law, and HIV and HCV rapid testing. Fourth, there will be significant potential benefits to science because the study will provide important information about intervention delivery with high-risk PWUD in rural areas who otherwise face enormous challenges to service utilization. The study will also provide information, which can be used to improve the reach and scope of evidence-based interventions during the transition from jail to community re-entry. Finally, the project will generate important information related to the feasibility of interventions for rural PWUD.

**Comparison group participants:** Although comparison group participants will receive fewer benefits from study participation compared to intervention participants, they will receive greater benefits than their counterparts in the general public who do not participate. The current "treatment as usual" condition for most individuals re-entering the community from jail, especially individuals not entering parole/probation supervision, is that they receive no or very limited overdose education. Given the high risk of overdose post-release, we will conduct a pre-release overdose intervention with the comparison cohort. Overdoses are not a primary study outcome, and it would be unethical to withhold overdose education from this cohort. Specifically, comparison group participants will complete an interactive training with animated scenarios and narration on preventing, recognizing, and responding effectively to an opioid OD, accompanied by information about Kentucky's Good Samaritan Law and Naloxone Access Law. The training covers how to recognize and respond to an overdose and how to administer naloxone. Individuals will also receive a Community Resource Guide to be left with their personal effects that they receive upon release.

This important study will advance knowledge on the delivery of an evidence-based intervention for high-risk, hard-to-reach, vulnerable rural PWUD who have traditionally been less likely to engage in formal treatment services. Innovation is heightened by the use of rural jails for recruiting and screening high-risk rural PWUD. The overall aim of this study is to decrease substance use, HIV/HCV risk behaviors, and improve access to treatment and harm reduction services through the use of a REHN. The long-term goal of this study is to improve the quality of health of high-risk, underserved populations.

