**b) Describe what measures will be taken to prevent intervention by prison authorities in the selection process:**

Consistent with IRB protocol #12-0372 and #43520, jail staff may monitor participant entry and exit into the attorney-client or visitation room for the screening and interview process, but no jail staff will be present for the confidential interviews. These rooms have a video camera (but no audio recorder), and staff will be trained to ensure that the participant's back is to the camera.

**Condition 4.** Parole boards cannot take into consideration a prisoner's participation in research. Informed consent must state participation will not impact parole.

**Describe what measures are in place to ensure parole boards are not influenced by prisoners' participation in research and how prisoners will be told their participation (or refusal or withdrawal from) will not impact parole:**

Based on our current study, we anticipate that most of our participants will be on probation rather than parole. However, confidentiality issues will be stressed during informed consent and will include the description of a federal Certificate of Confidentiality. Parole boards will not be aware of the participants' participation unless the person discloses it to the board. The informed consent states that participation while incarcerated will not affect probation, parole, or relationships with other agencies. Participants will also be assured that their screening results, study participation, and study data will not be made available to any representative of the jail or criminal justice system. Consent form language reflects this emphasis on participant confidentiality.

**Condition 5.** For studies that require follow-up, provisions are made including consideration for the length of individual sentences; informed consent must reflect provisions for follow-up.

**Describe what provisions have been made for follow-up and how this information will be relayed to the prisoner participants:**

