The REHN will provide a brief overview of the study and of the certificate of confidentiality. After the overview, participants will have the ability to ask the REHN questions. Before providing the screening surveys to the group, the REHN will then read the Screening Survey Cover Letter (attached in Informed Consent section) aloud, and participants will be given a hard copy. The cover letter will describe the risks and benefits of taking part in the screening, and will note in particular that (1) a certificate of confidentiality protects their data; and (2) their decision about participating has no bearing on their legal status. It will review the contents of the screening form, and the screening's anticipated duration. There will be no screening items capturing information that might require mandated reporting. Individuals will have time to ask the REHN questions about the screening process. Individuals who are interested in being screened can complete the survey and keep a copy of the cover letter. Of note, the KY Department of Corrections does require that all incarcerated individuals complete a general DOC consent form (see DOC Consent Form attached in Informed Consent section) granting permission to participate in research and require that a copy of that consent form be deposited with the KY DOC headquarters. To protect participant confidentiality and avoid revealing to DOC staff who screened eligible and participated, we will administer the DOC consent form to all individuals attending the study overview session, rather than only to those who screen eligible. Therefore, jail officials and administrators who maintain a copy of those forms will not be able to decipher which participants screened eligible, participated, or refused to participate.

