
At the group sessions, staff will provide a brief overview of the study, including describing the certificate of confidentiality and eligibility screening process. After the overview, participants will have the ability to ask the REHN questions. Following questions, the REHN will distribute paper copies of the screening survey (see Screener Appendix in Data Collection section) with a cover letter appended describing risks, benefits, and procedures involved in completing the screener (see Informed Consent section). The REHN will read the cover letter, screener instructions, and questions aloud to the group to support low-literate individuals. Individuals who consent will complete the screener. The screening survey will include questions to collect full name and date of birth so that staff can extend invitations (via jail staff) to those who are eligible to meet with them to learn more about the study, go through the consent process, and complete a study intake.

The REHN will collect the screeners, thank the prospective participants for screening, remind them that those who are eligible will be contacted later in the day to schedule a one-on-one appointment with the staff person to review the consent form, discuss the study, and if consent is granted, complete the intake process for the study (described below).

For individuals who participate in the screening session, who meet all eligibility criteria except "be incarcerated in a local jail and expected to be released in <21 days" but are interested in participating in the study, we will obtain their permission to contact them again closer to their release date to see if they are still interested in the study. If permission is provided, the REHN assigned to the local jail will work closely with the jailer regarding the individual's release date and to arrange a time to meet with the potential participant again. The REHN will confirm the individual is still interested in the study; if so, the screening form will be completed again, ensuring the individual meets the eligibility criteria. If all criteria are met, the REHN will review the consent form, discuss the study, and if consent is granted, complete the intake process for the study.

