During the recruitment session, staff will provide a brief overview of the study (recruitment presentation text) including describing the certificate of confidentiality and eligibility screening process. The jail staff will remain in the room. After the overview, participants will have the ability to ask the REHN questions. If the individual is interested in screening for the project, the individual will sign the DOC consent and the jail staff will sign as well. The jail staff will then leave the room and the REHN will continue with the screening process including reading the screener cover letter, completing the screener form, and completing the applicable county quiz, ensuring the individual is from the study county. If the individual is eligible, the REHN will immediately conduct the informed consent process. If the individual is not eligible, the REHN will let them know that they are not eligible and the session will end.

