#### COVID-19 Policies

Pre-Release Assessment (Session 1). We will work closely with each jail, providing them with a stack of Pre-Release Assessment packets. If an individual is eligible, agrees to participate in the project, and provides verbal consent, the REHN will move immediately to the Pre-Release Assessment (Session 1). If time does not permit, then the REHN will work with the jail staff to reschedule this session. During this assessment, the REHN will:

- 1) Read the script designed to build rapport with the participant given the session will be less personable than an in-person session.
- 2) Complete the Baseline Part 1 survey.
- 3) Share the How to Use Narcan (Naloxone) Educational Video. For phone interviews, the REHN will read aloud the Care2Hope Narcan

Patient Brochure and answer any questions the participant might have. This pamphlet is new and provided in all attachments. The REHN will explain to the participant that, at their first in-person meeting, the REHN will play the How to Use Narcan (Naloxone) Educational Video

- 4) Read the Good Samaritan Law document and answer any questions the participant might have.
- 5) Complete the Locator Form with the participant.
- 6) Schedule the second Pre-Release Assessment within 7 days of the first assessment.

Following the session, The REHN will work with jail staff to let them know which individuals need the Pre-Release Assessment packet. Jail staff will add the packet to the participant's personal belongings. The packet will include the following:

• A business card with the contact information for the REHN on it with a note letting the participant know that they should contact the REHN to set-up their post-release visit and to get their incentive card mailed to them if they elected to not get their incentive placed on their commissary.

- How to use Narcan (Naloxone) Patient Brochure
- Good Samaritan Law Handout
- Resource guide
- How to Use your Incentive Card Handout
- Certificate of Confidentiality One-Pager

Pre-Release Assessment (Session 2). During this session, the REHN will complete the Baseline Part 2 survey with the participant via Zoom or by phone.

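### Incarcerated participants are to be assured that jail staff will not learn their screening results or participation, but the routine jail procedures show jail staff who is eligible and who has enrolled

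*Combined protocol and SAP*

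**What the plan says.** Three places give the assurance, with different scope.

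- **Prisoners, Section 2, Condition 4.** The assurance to participants reads: "their screening results, study participation, and study data will not be made available to any representative of the jail or criminal justice system". The section adds that the consent form reflects this emphasis.
- **Informed Consent Process.** The statement is limited to what the Department of Corrections (DOC) consent forms reveal: "jail officials and administrators who maintain a copy of those forms will not be able to decipher which participants screened eligible".
- **Potential Risks & Benefits (under Benefits).** The same statement appears without that limit: "jail officials and administrators will not be able to decipher which participants screened eligible, participated, or refused to participate". The mechanism offered is that "we will administer the DOC consent form to all individuals attending the study overview session, rather than only to those who screen eligible".

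The procedures are set out elsewhere. Under Subject Recruitment Methods & Advertising, names and dates of birth are collected on the screener "so that staff can extend invitations (via jail staff) to those who are eligible to meet with them". Under the COVID-19 Policies of Research Procedures, after the first assessment, "The REHN will work with jail staff to let them know which individuals need the Pre-Release Assessment packet".

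**The concern.** For someone in jail, the people most able to act on knowledge of drug use are those running the jail. The assurance covers two facts, the screening result and taking part, and several planned steps pass one or both to jail staff. These are the ordinary logistics of the study and would happen even if nobody made a mistake.

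Two things are at stake. One is the accuracy of what an incarcerated person is told before deciding. The other is exposure to a harm the plan itself recognises. Condition 2 of the Prisoners section names disclosure of information beside distress as the risks. Potential Risks & Benefits names breach of confidentiality and lists stigma and loss of job or housing as consequences. Data and Safety Monitoring lists violation of confidentiality as a possible adverse event.

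**Working it through.** No arithmetic applies. The check sets the assurance beside each jail procedure and asks what jail staff learn.

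**Step 1: what each procedure shows jail staff**

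| Procedure | Where | What jail staff learn |
|---|---|---|
| Invitations to the one-on-one session go through jail staff, to eligible people only | Prisoners, Condition 3(a); Subject Recruitment Methods | Who screened eligible |
| Eligible people fix the time with facility staff | Prisoners, Condition 3(a) | Who screened eligible |
| Jail staff may watch entry to and exit from the room | Prisoners, Condition 3(b) | Who attended |
| A sealed envelope with the appointment card is left with jail staff for the person's belongings | Prisoners, Condition 5; Research Procedures, Session 1 | Who enrolled |
| Where jail leadership allows, naloxone is handed to jail staff for participants | Research Procedures, Session 1 | Who enrolled |
| Baseline payments ($25 and $10) may go to the commissary account | Prisoners, Section 1; Payment, including its COVID-19 part | Possibly who took part, if deposits are visible to those running the accounts |
| Remote route: the navigator tells jail staff who needs the packet | Research Procedures, COVID-19 Policies | Who enrolled |

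The remote packet goes to people who have consented and been through the first assessment. It includes a Certificate of Confidentiality sheet and a handout on using the incentive card. No seal is mentioned for it.

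**Step 2: what eligibility implies.** Study Population gives two jail routes. On the main one, a person must be an adult, tied to a study county, near release, and have used opioids to get high or injected a drug in the 30 days before incarceration. A jail would ordinarily know the first three already, so the new information is the drug use. The other route, for members of the earlier longitudinal survey, does not state that criterion.

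**Step 3: the assurance item by item**

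- *Eligibility:* revealed by the in-person invitation and scheduling.
- *Participation:* revealed by the envelope and naloxone in person, and by the packet notice in the remote procedure.
- *Refusal:* not reported. It could be inferred from an eligible invitee for whom nothing is later left.
- *Screening and survey answers, other study data:* nothing in these steps hands them to jail staff.

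**Step 4: does the safeguard reach these channels?** Having every overview attendee sign the DOC form prevents the stack of forms from identifying eligible people. It does nothing about invitations, scheduling, envelopes, naloxone, payments or packets.

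**The case against.** The strongest reply is about scope. In Potential Risks & Benefits the sentence is a conclusion drawn from the DOC-form procedure and addressed to the IRB. The Informed Consent Process carries the explicit limit, and the participant assurance in that same risk section concerns survey answers. Read that way, the DOC-form statement is defensible. This stands for that sentence, but Condition 4 of the Prisoners section is not limited to the forms. It is a promise to participants, and it names screening results and participation.

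The plan is also candid in places. It says jail staff may monitor the room, it calls the envelope tamper-evident and tape-sealed, and it admits that jail Zoom follow-up cannot be fully confidential. A seal hides the contents but not the recipient. Consent, quiz failure and refusal take place in a room closed to jail staff, so an invitation alone does not show enrolment.

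A reader might infer more than the documents support:

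- *That confidentiality is the main named risk.* Condition 2 pairs it with distress, and the risk section puts psychological risk first.
- *That the consent form itself misleads.* The form is not among the documents. Only its emphasis is described.
- *That these disclosures would never be logged or reviewed.* The procedures are in the IRB application, the DSMB reviews the protocol and consent process, and identified breaches go to the IRB at once.
- *That the remote DOC signing defeats the safeguard.* There "the individual will sign the DOC consent and the jail staff will sign as well", and only if the person wants screening, which departs from having all attendees sign. But signing comes before screening and jail staff then leave, so the form still does not show who was eligible or enrolled.

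**Conclusion.** The contradiction holds. Condition 4 promises that jail representatives will not be given screening results or participation, and the plan's own steps reveal eligibility on the in-person route and participation on both routes. Disclosure, one of the main named risks, is therefore built into the procedures for jail recruits. Community recruits are not affected.

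The point concerns participant protection and accurate consent. It changes no outcome, analysis or sample size. Its reach is everyone who screens eligible in person in jail and everyone who enrols there by either route. The packet notice applies only to the remote procedure. The split between jail and community recruitment is not stated, so any headcount would be a guess.

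The conclusion assumes that staff who pass on invitations or handle envelopes count as representatives of the jail, which is the plain meaning. The sensitivity of what they learn also assumes that they know or can work out the screening criteria. In the remote procedure they sit through the overview, which covers the eligibility screening process.

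**What to change.** 1. **Reconcile the wording.** Bring Condition 4 into line with the invitation, envelope, naloxone and packet procedures. Limit the sentence in Potential Risks & Benefits to what the DOC forms reveal, as the Informed Consent Process already does. Any matching consent wording should say that jail staff may learn who is invited back, who attends, who is paid through commissary, and for whom a packet or naloxone is left, but will not see screening or survey answers or other study data. This step is essential, because it resolves the contradiction even where jail logistics cannot change.

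2. **Reduce the exposure.** Leave the same plain sealed envelope (resource guide, naloxone brochure, Good Samaritan handout, navigator contact card) for everyone who attends an overview or recruitment session. Give the Certificate of Confidentiality sheet and incentive-card handout at the first post-release contact, not in the packet held by the jail.

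The second step does not remove the signals from invitations, room monitoring, commissary payments or jail-held naloxone, so the wording in the first step must cover them. The remote DOC-form step should stay as it is. Having every remote attendee sign would make people who decline screening sign a research-permission form in front of jail staff.

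The cost is a protocol and consent amendment and some more printed envelopes. The franker wording is less reassuring and may slightly lower uptake.
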